7.3.2.1. Overall Summary of Adverse Events

An overall summary of TEAEs and treatment-emergent SAEs (TESAEs) will include summaries of events (n) and number of patients with events (n, %).

Within each summary category (TEAEs, TESAEs) the following subcategories will also be summarized, as appropriate:

- At Least 1 TEAE
- At Least 1 Severe TEAE
- At Least 1 Related TEAE (possibly related or related to study drug)
- At Least 1 TEAE Leading to Withdrawal / Discontinuation from the Study
- At Least 1 IAR
- At Least 1 Serious TEAE

Additionally, the number and percentage of patients who died on study will be presented.

7.3.2.2. AEs and SAEs by System Organ Class (SOC) and Preferred Term (PT)

The number of TEAEs and the number and percentage of patients with events will be descriptively summarized and presented by SOC and PT. Patients are counted once in each SOC and PT. Percentages will be based on the total number of treated patients by Part C dose assignment and overall for each visit assessed.

The number of Serious TEAE's and the number and percentage of patients with events will be descriptively summarized and presented by PT. Patients are counted once in each PT. Percentages will be based on the total number of treated patients by Part C dose assignment and overall for each visit assessed.

All AEs will be presented in by-patient listings.

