6.3. Safety Set

The Safety Analysis Set, defined as all patients for whom informed consent has been obtained, who have a confirmed diagnosis of MPS IIIB, and who have received any amount of SBC-103, will be used to summarize all safety and tolerability data.

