7.3.2. Adverse Events (AEs)

Information will be summarized on all AEs that began at any time from the date of first study dose in Part A through the last procedure at the last study visit. Adverse events will be classified by the study Investigator into one of the following relations to study drug: not related, unlikely related, possibly related or related to study drug. For reporting purposes, "related" events will include all AEs assessed by the Investigator as: possibly related, or related to study drug.

All AEs captured in the eCRF will be coded using the Medical Dictionary for Regulatory Activities (MedDRA) coding system and displayed in tables and data listings using System Organ Class (SOC) and Preferred Term (PT). All AEs will be coded using the MedDRA, version 13.1 or higher.

Severity of AEs will be graded on a 3-point scale (mild, moderate and severe) based on the definitions, developed from Clinical Data Interchange Standards Consortium (CDISC) Study Data Tabulation Model (SDTM) standard terminology v3.1.1 (see Protocol Section 7.1.1).

Adverse event incidence will be reported based on the concept of treatment emergence for the purposes of this analysis. Any AE that occurs after the first dose of SBC-103 in Part A is considered a treatment emergent adverse event (TEAE) for this study.

Adverse events are summarized by patient incidence rates; therefore, in any tabulation, a patient contributes only once to the count for a given AE.

The number of events, as well as the number and percentage of patients with a TEAE, will be summarized by Part C dose assignment and overall, cumulatively over the entire study and separately for Part C.

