7.3.3.3. Other Safety Parameters of Special Interest

7.3.3.3.1. Antidrug Antibody (ADA)

Assays testing for screening, confirmed, neutralizing ADA will be performed and ADA titers will be measured for neutralizing antibodies. For this analysis, confirmed ADA assay results will be descriptively presented by ADA status (Positive, Negative) as the proportion of patients, n (%), with measurable confirmed antibodies to SBC-103 by Part C dose assignment and overall for each assessed visit. Neutralizing antibodies for confirmed positive cases will also be presented.

ADA titer result statistics will be descriptively presented by ADA status, visit, Part C dose assignment and overall.

The number and percentage of patients with Infusion-Association Reactions (IARs) adverse events by MedDRA System Organ Class, Preferred Term, and ADA positivity will be presented along with the number of IAR events. If a patient experienced more than one event in a given SOC, that patient is counted once for that SOC. If a patient experienced more than one event with a given PT, that patient is counted only once for that PT.

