9.3.2. Randomization

Parts A and B were open label and non-randomized with no requirement for blinding.

In Part C, subjects are randomized such that at least 1 subject from each dose assignment in Part A received SBC-103 at 5 mg/kg and at least 1 subject from each dose assignment in Part A received SBC-103 at 10 mg/kg. Thus each of the assigned dose levels from Part A is represented in each of the 2 dose levels being studied in Part C.

As noted in the CSP Section 1.4.1, a total of 11 subjects enrolled in this study; 5 of these randomized to receive 5 mg/kg QOW and 6 randomized to receive 10 mg/kg QOW.

Details of the randomization are provided in a randomization specification document, which is maintained by the Sponsor.

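### SAP 7.3.2.2 ties the AE and serious AE percentage base to visits, which contradicts the cumulative tables planned in SAP 7.3.2 and leaves the denominator unclear

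*SAP*

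**What the plan says.** SAP 7.3.2 sets the frame for all AE tables. It says of the TEAE results, given both as events and as patients affected with percentages, that they "will be summarized by Part C dose assignment and overall, cumulatively over the entire study and separately for Part C". The counting rule is that "in any tabulation, a patient contributes only once to the count for a given AE".

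SAP 7.3.2.2 then covers two tables: TEAEs by SOC and PT, and serious TEAEs by PT. For the first it says "Patients are counted once in each SOC and PT", and for the second it repeats the rule at PT level. For each table it gives the same percentage base: "Percentages will be based on the total number of treated patients by Part C dose assignment and overall for each visit assessed".

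Three other places bear on the denominator:

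- SAP 6.3 defines the Safety Set as consented patients with a confirmed diagnosis "who have received any amount of SBC-103, will be used to summarize all safety and tolerability data". Membership does not depend on any visit.
- SAP 9.3.2 gives the group sizes: of 11 subjects, "5 of these randomized to receive 5 mg/kg QOW and 6 randomized to receive 10 mg/kg QOW".
- SAP 7.3.3.3.1 presents the proportion of patients "with measurable confirmed antibodies to SBC-103 by Part C dose assignment and overall for each assessed visit". That is almost the same wording, used for samples that are taken at scheduled visits.

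**The concern.** A patient-incidence table needs a numerator and a denominator that cover the same period. The planned periods are the whole study and Part C; neither is a visit. A rule that defines the percentage base by visit cannot be applied to such a table without first choosing a visit, and the SAP names none.

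Two features make this more than a slip of style. First, SAP 9.4.2 says data are tabulated under the visit recorded on the eCRF, so a programmer who hesitates over 7.3.2.2 finds a second text pointing towards visits. Second, the SAP has reduced the safety report. Laboratory data and vital signs are listings only (SAP 4.1.4), ECG is dropped (SAP 5.2.4.2), and relationship and severity by SOC and PT are left to listings (SAP 7.3.2.3 and 7.3.2.4). The SOC/PT and serious-PT tables are thus among the few numerical summaries of the primary endpoint, and in groups of 5 and 6 the loss of one or two patients from a denominator moves a percentage visibly.

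**Working it through.** Neither document states an AE percentage, so there is no figure of the plan's own to reproduce. The check has two parts.

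**1. Do the sections fit together?**

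- Period: SAP 7.3.2 specifies "cumulatively over the entire study and separately for Part C". No by-visit AE table is planned.
- Numerator: one count per patient per SOC and PT (SAP 7.3.2 and 7.3.2.2).
- Collection: AEs are marked as continuous in every schedule of assessments, and Protocol 7.3 has them recorded by date, or by date and time within 24 hours of an infusion. The SAP has no rule that assigns an AE to a visit.
- Denominator: SAP 7.3.2.2 names the treated patients per column and then qualifies that number by visit.

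The first three items describe a table over a period. Only the qualifier in the fourth refers to visits, and it does not fit the other three.

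**2. How much could it matter?**

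Inputs: group sizes 5 and 6 (SAP 9.3.2), with 5 + 6 = 11 overall. Assumption: all randomized subjects were dosed in Part C. The number m counted at a visit is also assumed, because the documents give no such counts.

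Formulas: fixed base, 100 × x / N; literal visit base, 100 × x / m, where x is the cumulative number of patients with the event.

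| Group | x | Fixed base | Literal visit base (m hypothetical) |
|---|---|---|---|
| 5 mg/kg | 1 | 1/5 = 20.0% | 1/4 = 25.0%; 1/3 = 33.3% |
| 5 mg/kg | 2 | 2/5 = 40.0% | 2/3 = 66.7% |
| 10 mg/kg | 1 | 1/6 = 16.7% | 1/4 = 25.0%; 1/3 = 33.3% |
| 10 mg/kg | 3 | 3/6 = 50.0% | 3/4 = 75.0%; 3/2 = 150.0% |
| Overall | 1 | 1/11 = 9.1% | 1/10 = 10.0%; 1/8 = 12.5% |

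When m = N the two columns agree. When m is below N the literal base inflates the percentage, and when m is below x the result exceeds 100%, which is impossible for an incidence.

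Could m be below N? SAP 9.4.1 says subjects enter Part C at different times. SAP section 4 gives Part C follow-up of 90 to 110 weeks and reports that development was stopped in July 2017. Fewer patients at the last Part C visits is therefore plausible, but its extent cannot be taken from the documents.

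**The case against.** The strongest reply is that the sentence already contains a usable denominator. It names the total number treated, by dose assignment and overall, and nothing says that a patient absent from a visit leaves that total. Together with the Safety Set definition and the randomized numbers, the natural denominators are 5, 6 and 11. On this view the visit qualifier is a stray phrase that resembles the ADA wording and does no harm. That is a reasonable guess at the intention, but it works only by ignoring part of a stated rule.

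A second reply is that a by-visit presentation may be meant, with numerator and denominator both specific to the visit. Percentages would then stay at or below 100%, and the once-only count could be kept within each visit's tabulation. This is coherent in itself, but SAP 7.3.2 plans no such table and the SAP gives no rule for allocating AEs to visits.

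A third reply is that the consequence is limited, and this stands. The analysis is descriptive, without p-values (SAP 7.2.1.4). Patient counts appear beside the percentages, all AEs are listed by patient, and a figure above 100% would be noticed. The overall AE summary in SAP 7.3.2.1 does not carry the visit qualifier, so only the SOC/PT and serious-PT breakdowns are affected.

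A reader might go further and infer that the planned incidences are wrong, or that few children reach the late visits. The documents support neither. The first needs the qualifier to be applied literally to cumulative counts with some treated patients left out; the second needs visit counts that are not given.

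**Conclusion.** The point holds as a contradiction within the SAP. The percentage base in 7.3.2.2, stated twice, does not match the cumulative and Part C-wide tables in 7.3.2 and cannot be applied as written. It should be corrected because it is an explicit rule for tables of the primary endpoint, not merely an absent detail.

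The possible effect on one patient in the 10 mg/kg group is a move from 16.7% to 25.0% if 4 of the 6 are counted at the visit. The effect is nil if all treated patients are counted. Every figure other than those on bases of 5, 6 and 11 rests on an assumed visit count, and the fixed-base Part C figures assume that all randomized subjects were dosed in Part C. No type I error or power is involved.

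**What to change.** In SAP 7.3.2.2, delete the closing visit qualifier (the last four words) from both percentage sentences, and state the denominators:

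- Whole-study tables: Safety Set patients in each Part C dose-assignment column, and overall.
- Part C tables: patients who received at least one Part C dose, by column and overall.

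The two need separate statements because they may differ. Protocol 4.3.4 requires at least 4 doses at 3 mg/kg before Part C, and Protocol 3.1.2 keeps subjects who cannot tolerate these in Part B. Keep by-visit denominators for the ADA proportions only.

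The cost is two edited sentences and a short statement of the denominators. Data collection and trial conduct are unaffected.

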7.3.2.3. AEs and SAEs by SOC, PT, and Relationship

Individual patient AE/SAE data for Relationship to Study Drug and Relationship to Study Procedures is presented in the by-patient AE listings.

7.3.2.4. AEs and SAEs by SOC, PT, and Severity

Individual patient AE/SAE data for severity is presented by-patient AE listings.

7.3.2.5. Deaths, Other SAEs, and Other Significant Adverse Events

Deaths and other SAE's will be identified by the data presented in the by-patient listings of AEs.

7.3.2.5.1 Other Significant Adverse Events

Procedure-related AEs will be identified by the relationship to study procedures data presented in the by-patient listings of AEs.

7.3.2.5.2. Infusion-Associated Reactions

Infusion-associated reactions (IARs) will be considered AEs of special interest (AESIs). An AE will be considered an IAR if it meets either of the following criteria:

- The Investigator checks "Yes" to the question "Is AE an IAR?" on the AE eCRF.
- The AE (diagnosis and/or symptom) occurs between the start of the infusion up to 4 hours after the infusion and is assessed by the Investigator as at least possibly related to Investigational Medicinal Product (IMP).

Note that several AEs may be associated with 1 IAR observed with SBC-103 administration; each AE is captured as a separate event. The number and percentage of patients who experience any IAR and the number of IARs reported over the course of the study will be summarized. Any patient who experiences an IAR is only counted once regardless of the number of associated events. Patients may be counted more than once if IARs occur on more than 1 dosing day.

Summaries of AEs that comprise an IAR will be displayed by MedDRA PT. Each patient will be counted only once within each PT.

A by-patient data listing of all AEs will be presented.

7.3.3. Other Safety

7.3.3.1. Analyses for Laboratory Tests

The clinical laboratory data include hematology, chemistry, urinalysis (including coagulation, renal function and liver function), CSF findings and CSF-AI ratio. All clinical laboratory data will be listed.

Clinical laboratory values by time of assessment will be expressed in International System of units (SI units) in data listings. Unscheduled lab test results will also be presented in the data listings. Abnormal lab values will be flagged with "H"/"L" or "HIGH"/"LOW" for out of range values, and an asterisk for clinical significance in the data listings.

Patient data for clinical laboratory data will be presented in listings by Part C dose assignment, patient number and visit.

7.3.3.2. Vital Signs

Vital signs include systolic blood pressure, diastolic blood pressure, heart rate, respiratory rate, and body temperature. A listing of vital signs will be presented by patient number, vital sign parameter, vital sign value, and visit.

7.3.3.3. Other Safety Parameters of Special Interest

7.3.3.3.1. Antidrug Antibody (ADA)

Assays testing for screening, confirmed, neutralizing ADA will be performed and ADA titers will be measured for neutralizing antibodies. For this analysis, confirmed ADA assay results will be descriptively presented by ADA status (Positive, Negative) as the proportion of patients, n (%), with measurable confirmed antibodies to SBC-103 by Part C dose assignment and overall for each assessed visit. Neutralizing antibodies for confirmed positive cases will also be presented.

ADA titer result statistics will be descriptively presented by ADA status, visit, Part C dose assignment and overall.

The number and percentage of patients with Infusion-Association Reactions (IARs) adverse events by MedDRA System Organ Class, Preferred Term, and ADA positivity will be presented along with the number of IAR events. If a patient experienced more than one event in a given SOC, that patient is counted once for that SOC. If a patient experienced more than one event with a given PT, that patient is counted only once for that PT.

7.3.3.3.2. ECG

Analyses of ECG data will not be included in the CSR.

8. **REFERENCES**

Statistical Analysis Plan {01 Sep 2017, Version 1.0}

9. **APPENDICES**

9.1. Schedule of Study Assessments

Proprietary and Confidential

Alexion Pharmaceuticals

{Protocol: NGLU-CL02 21 Jan 2016 (Amendment 7)}

Statistical Analysis Plan {01 Sep 2017, Version 1.0}

9.1.1. Schedule of Study Assessments (Part A, Initial Therapy)

					Schedu	le of Stud	ly Assessr	nents								
						Pa	rt A: Initi	al Therap	y							Time Off
Assessments	Screening	Day 0***	Day 1	Week 2	Week 4	Week 6	Week 8	Week 10	Week 12	Week 14	Week 16	Week 18	Week 20	Week 22	Week 24	Week 26
Visit Window (Days)*	-28 to 0 ^{**}	-4 to 0		±5	±5	±5	±5	±5	±5	±5	±5	±5	±5	±5	±5	
Informed Consent/Assent	Х															
Inclusion/Exclusion Criteria	Х															
Medical History/ Demography	х															
Physical Examination	Х	X ^P	Х		XP		XP		XP		XP		XP		XP	
Height and Weight	Х	XP			XP		XP		XP		XP		XP		XP	
Vital Signs ¹	Х	Х	х	х	х	х	х	х	х	х	х	х	х	х	х	
12-lead ECG (Triplicate ²)	х	XP							XP						XP	
FDNA	Х														Х	
Vineland-II, BSID-III, KABC-II, BOT-2 Brief Form, CSHQ, CCC-2, SBRS, ZBI 12-item, SF-10 ³	X ³														X ^p	
NAGLU Enzyme Activity ⁴	Х															
NAGLU Genotype ⁵	Х															
DNA Sample ⁶	Х															
Hematology, Serum Chemistry (including					P		0				b				6	
Coagulation ⁷), Urinalysis ⁸	Х	XP	Х		X ^P		X ^P		X ^P		XP		X ^P		XP	
Pregnancy Test (Urine) ⁹	Х	XP			X ^P		X ^P		XP		X ^P		X ^P		X ^P	
Serum and Urine Heparan Sulfate (Total and NRE) ¹⁰	x	XP			XP		XP		XP		XP		XP		X ^P	
Serum Ferritin and Chitotriosidase ¹¹	x	XP			X ^P		XP		XP		X ^P		X ^P		X٩	
Plasma Glutamic Acid and Glycine ¹¹	х	X ^P			XP		XP		XP		XP		XP		X٩	
Serum Biomarkers (Exploratory, including IgG and Inflammatory Markers)		X ^P			X ^P		X ^P		XP		X٩		X ^P		X٩	
Blood Pharmacokinetic Profile ¹²		х							х						х	
SBC-103 ADA ¹³		XP			XP		XP		XP		XP		XP		XP	

Statistical Analysis Plan {01 Sep 2017, Version 1.0}

					Schedu	le of Stud	y Assessm	nents								
						Р	art A: Ini	tial Therap	рγ							Time Off
Assessments	Screening	Day 0***	Day 1	Week 2	Week 4	Week 6	Week 8	Week 10	Week 12	Week 14	Week 16	Week 18	Week 20	Week 22	Week 24	Week 26
Visit Window (Days)*	-28 to 0**	-4 to 0		±5	±5	±5	±5	±5	±5	±5	±5	±5	±5	±5	±5	
General Anesthesia/Sedation ¹⁴		X٩							XP						XP	
Lumbar Puncture ^{7,14,15}		XP							XP						XP	
Heparan Sulfate (Total and NRE) in CSF		X٩							X ^P						XP	
Calbindin D, HGF, Tau, pTau, Amyloid β, Albumin, IgG in CSF ¹⁴		X۶							X٩						XP	
Glutamic Acids and Glycine in CSF		X٩							XP						XP	
Routine Findings (Cell Counts, Glucose, Protein) in CSF		X ^P							X٩						XP	
SBC-103 in CSF		X ^p							XP						XP	
Structural and Diffusion MRI ¹⁴		X ^P													XP	
SBC-103 Dosing		Х		Х	Х	Х	Х	Х	Х	Х	Х	Х	Х	Х	Х	
Telephone call ¹⁶				х	х	х									х	
Part B Eligibility Assessment																x
Adverse Events ¹⁷			•		•		C	ONTINUO	US	•	•		•			•
Concomitant Medications ¹⁸								ONTINUO								

Key: ADA = anti-drug antibodies; BOT-2 Brief Form = Bruininks-Oseretsky Test of Motor Proficiency, Second Edition, Brief Form; BSID-III = Bayley Scales of Infant and Toddler Development, Third Edition; CCC-2 = Children's Communication Checklist, Second Edition; CSF = cerebrospinal fluid; CSHQ = Children's Sleep Habits Questionnaire; ECG = electrocardiogram; FDNA = Facial Dysmorphology Novel Analysis; HGF = hepatocyte growth factor; IgG = immunoglobulin G; KABC-II = Kaufman Assessment Battery for Children, Second Edition; MRI = magnetic resonance imaging; NAGLU = alpha-N-acetylglucosaminidase; NRE = non-reducing end; SBRS = Sanfilippo Behavior Rating Scale; SF-10 = 10-item Short Form Health Survey for Children; Vineland-II

= Vineland Adaptive Behavior Scales, Second Edition; ZBI = Zarit Burden Interview, 12-item.

* All study visits will be scheduled relative to Day 0; infusions must be administered at least 10 days apart.

** Subjects who are unable to complete all Screening procedures within 28-day window may be re-screened. See Section 4.7.

*** Day 0 assessments may be completed over 5 days (starting on Day -4) provided that all eligibility assessments are completed prior to the commencement of any Day 0 procedure (ie, any invasive procedures, including general anesthesia or sedation, lumbar puncture, and MRI). Subjects will be monitored for at least 24 hours in an in-patient setting at the Day 0 visit. Documentation/confirmation of eligibility must be provided to the Sponsor and is subject to Sponsor review and agreement. At Day 0, the lumbar puncture (including the initiation of sedation/anesthesia) shall not commence until the site receives the coagulation results, confirms that a subject continues to meet eligibility, and provides such documentation to the Sponsor for review and agreement.

X^P Assessments to be performed pre-dose.

1. Vital signs will be taken pre-dose (within approximately 30 minutes), approximately every 15 minutes during infusion and approximately every 15 minutes for 2 hours after completion of the infusion. On Day 1, vital signs will be obtained prior to discharge. Vital signs will be obtained after any lumbar puncture as per site standard of care. In addition, a baseline blood pressure measurement should be taken in triplicate at screening or prior to SBC-103 administration on either Day 0 in Part A or the subject's next scheduled infusion (see Section 5.1.7).

Statistical Analysis Plan {01 Sep 2017, Version 1.0}

- 2. 12-lead ECGs should be collected in triplicate (within 5 minutes), when possible during Part A of the study only.
- 3. If the identical assessment(s) were previously administered, historical results should be recorded. The Vineland-II, BSID-III or KABC-II, BOT-2 Brief Form, and CCC-2 should be administered in-person by an appropriately qualified professional.
- 4. NAGLU enzyme activity will be assessed by a central laboratory at Screening, irrespective of whether historical enzyme activity results are available from a local laboratory.
- 5. DNA sample for NAGLU genotype is required to confirm Diagnosis of MPS IIIB when a historical result is not available from the study central lab.
- 6. Performed where local regulations permit and subject to discretionary approval from each center's IRB/IEC and the consent/assent of the subject (and/or consent of the subject's parent or legal guardian).
- 7. The coagulation laboratory panel should be collected within 48 hours prior to performing the lumbar puncture, and the results should be available prior to sedating/anesthetizing the subject or performing the lumbar puncture. The procedure (including the initiation of sedation/anesthesia) will not commence until the site receives these results and confirms that it is safe for the subject to receive anesthesia/sedation and the lumbar puncture. To facilitate this process, all coagulation panels (as of 23 March 2015) will be drawn and analyzed locally rather than sent to the central laboratory for analysis.
- 8. If samples are taken within 3 days of Day 0, samples do not need to be repeated on Day 0. However, a Day 0 serum sample for albumin should be collected at the same time as the CSF collection, to enable calculation of CSF-AI. Central lab reference ranges will be used throughout the study, including in the event that labs are analyzed locally. All attempts should be made to draw lab samples for central lab analysis when samples are needed for local analysis.
- 9. If a urine sample is not able to be provided, a serum pregnancy test will be performed by a local laboratory.
- 10. If serum or urine heparan sulfate is collected within 7 days of Day 0, it does not need to be repeated at Day 0. All attempts should be made to collect a urine sample for heparan sulfate.
- 11. If serum ferritin, chitotriosidase and amino acid panel is collected within 7 days of Day 0, it does not need to be repeated at Day 0.
- 12. Refer to Section 5.2.1.3 for directions and timing of PK sampling.
- 13. In addition to time points indicated, obtain a sample for ADA determination anytime subject experiences a moderate or severe IAR during the next study visit (> 4 days after the IAR) and prior to the infusion.
- 14. Lumbar puncture and MRI procedures may be performed under general anaesthesia or light sedation, as clinically appropriate in accordance with local institutional procedures. If clinically indicated, subjects may also receive general anesthesia or sedation for central line placement for long-term vascular access, in accordance with institutional guidelines. When possible, the procedure to place the central line should be performed while the subject is already anesthetized or sedated for another study procedure. During study visits where CSF is collected that do not coincide with a serum chemistry sample per the SOA, a serum albumin should be collected in order to assess CSF-AI Index. After the lumbar puncture is completed, the subject should be observed as per institution standard practice.
- 15. Subjects should be observed following the lumbar puncture as per institution standard practice. Vital signs, adverse events and concomitant medications should be assessed before the subject is discharged from the site.
- 16. A follow-up telephone call will be made to the subject (or the subject's parent or caregiver) within 24 hours of the 2nd, 3rd, and 4th doses in Part A, and after the last dose of SBC-103 administered in the study (Week 24 or Early Termination) unless the subject has a scheduled follow-up visit.
- 17. All AEs should be followed until they have returned to baseline values or stabilized or until the Investigator and Sponsor or designee agree that follow-up is no longer necessary.
- 18. Information on all medications and treatments received by the subject within the 4 weeks preceding the Screening visit through the final visit will be recorded in the CRF.

Alexion Pharmaceuticals

Statistical Analysis Plan

{Protocol: NGLU-CL02 21 Jan 2016 (Amendment 7)}

{01 Sep 2017, Version 1.0}

9.1.2. Schedule of Study Assessments (Part B, Therapy at 1 and/or 3 mg/kg – Year 1)

					hedule of Stu	,		(h) 1 ac.:					
					Part B: Ther			1					
Assessments	Week 28	Week 30	Week 32	Week 34	Week 36	Week 38	Week 40	Week 42	Week 44	Week 46	Week 48	Week 50	Week 52
Visit Window (Days)*	+3	±5	±5	±5	±5	±5	±5	±5	±5	±5	±5	±5	±5
Physical Examination	XP		XP		XP		XP		XP		XP		XP
Height and Weight	XP		XP		XP		XP		X ^P		XP		XP
Vital Signs ¹	Х	Х	Х	Х	Х	Х	Х	Х	Х	Х	Х	Х	Х
12-lead ECG					Х								Х
FDNA													Х
Vineland-II, BSID-III, KABC-II, BOT-2 Brief Form, CSHQ, CCC-2, SBRS, ZBI 12-item, SF- 10 ²													х
Hematology, Serum Chemistry (including Coagulation ³), Urinalysis ⁴	X ^P				X ^P				X ^P				X ^P
Pregnancy Test (Urine) ⁵	XP		XP		XP		XP		XP		XP		XP
Serum and Urine Heparan Sulfate (Total and NRE)	XP				XP				X ^P				XP
Serum Ferritin and Chitotriosidase	XP				XP				XP				XP
Plasma Glutamic Acid and Glycine	X ^P				X ^P				X ^P				X ^P
Exploratory Serum Biomarkers, including IgG, Inflammatory markers	X ^P				X ^P				X ^P				X۶
Serum Pharmacokinetic Profile ⁶													Х
SBC-103 ADA ⁷	XP		XP		XP		XP		XP		XP		XP
General Anesthesia/Sedation ⁸	XP						XP						XP
Lumbar Puncture ^{3,8,9}	XP						XP						XP
Heparan Sulfate (Total and NRE) in CSF	XP						X ^P						X ^P
Calbindin D, HGF, Tau, pTau, Amyloid β, Albumin, IgG in CSF	XP						XP						XP
Glutamic Acids and Glycine in CSF	X ^P						X ^P						X ^P
Routine Findings (Cell Counts, Glucose, Protein) in CSF	X ^P						X ^P						X ^P
SBC-103 in CSF	XP						XP						X ^P
Structural and Diffusion MRI ⁸													XP

	Schedule of Study Assessments												
		Part B: Therapy at 1 and/or 3 mg/kg (Weeks 28 through 52)											
Assessments	Week 28	k 28 Week 30 Week 32 Week 34 Week 36 Week 38 Week 40 Week 42 Week 44 Week 46 Week 48 Week 50 Week 52											
Visit Window (Days)*	+3	3 ±5 ±5 ±5 ±5 ±5 ±5 ±5 ±5 ±5 ±5 ±5 ±5											±5
SBC-103 Dosing	Х	Х	Х	Х	Х	Х	Х	Х	Х	Х	Х	Х	Х
Adverse Events ¹⁰							CONTINUOU	5					
Concomitant Medications ¹¹		CONTINUOUS											

Key: ADA = anti-drug antibodies; BOT-2 Brief Form = Bruininks-Oseretsky Test of Motor Proficiency, Second Edition, Brief Form; BSID-III = Bayley Scales of Infant and Toddler Development, Third Edition; CCC-2 = Children's Communication Checklist, Second Edition; CSF = cerebrospinal fluid; CSHQ = Children's Sleep Habits Questionnaire; ECG = electrocardiogram; FDNA = Facial Dysmorphology Novel Analysis; HGF = hepatocyte growth factor; IgG = immunoglobulin G; KABC-II = Kaufman Assessment Battery for Children, Second Edition; NAGLU = alpha-N- acetylglucosaminidase; NRE = non-reducing end; SBRS = Sanfilippo Behavior Rating Scale; SF-10 = 10-item Short Form Health Survey for Children; Vineland-II = Vineland Adaptive Behavior Scales, Second Edition; ZBI = Zarit Burden Interview, 12-item.

* All study visits will be scheduled relative to Day 0; infusions must be administered at least 10 days apart. X^P Assessments to be performed pre-dose.

- 1. Vital signs will be taken pre-dose (within approximately 30 minutes), approximately every 15 minutes during infusion and approximately every 15 minutes for 2 hours after completion of the infusion. Vital signs will be obtained after any lumbar puncture as per site standard of care.
- 2. The Vineland-II, BSID-III or KABC-II, BOT-2 Brief Form, and CCC-2 should be administered in-person by an appropriately qualified professional.
- 3. The coagulation laboratory panel should be collected within 48 hours prior to performing the lumbar puncture, and the results should be available prior to sedating/anesthetizing the subject or performing the lumbar puncture. The procedure (including the initiation of sedation/anesthesia) will not commence until the site receives these results and confirms that it is safe for the subject to receive anesthesia/sedation and the lumbar puncture. To facilitate this process, all coagulation panels (as of 23 March 2015) will be drawn and analyzed locally rather than sent to the central laboratory for analysis.
- 4. Central lab reference ranges will be used throughout the study, including in the event that labs are analyzed locally. All attempts should be made to draw lab samples for central lab analysis when samples are needed for local analysis.
- 5. If a urine sample is not able to be provided, a serum pregnancy test will be performed by a local laboratory.
- 6. Refer to Section 5.2.1.3 for directions and timing of PK sampling.
- 7. In addition to time points indicated, obtain a sample for ADA determination anytime subject experiences a moderate or severe IAR during the next study visit (≥ 4 days after the IAR) and prior to the infusion.
- 8. Lumbar puncture and MRI procedures may be performed under general anaesthesia or light sedation, as clinically appropriate in accordance with local institutional procedures. If clinically indicated, subjects may also receive general anesthesia or sedation for central line placement for long-term vascular access, in accordance with institutional guidelines. When possible, the procedure to place the central line should be performed while the subject is already anesthetized or sedated for another study procedure. After the lumbar puncture is completed, the subject should be observed as per institution standard practice. Vital signs, adverse events and concomitant medications should be assessed before the subject is discharged from the site.
- 9. During study visits where CSF is collected that do not coincide with a serum chemistry sample per the SOA, a serum albumin should be collected in order to assess CSF-AI Index. After the lumbar puncture is completed, the subject should be observed as per institution standard practice.
- 10. All AEs should be followed until they have returned to baseline values or stabilized or until the Investigator and Sponsor or designee agree that follow-up is no longer necessary.
- 11. Information on all medications and treatments received by the subject within the 4 weeks preceding the Screening visit through the final visit will be recorded in the CRF.

Alexion Pharmaceuticals

{Protocol: NGLU-CL02 21 Jan 2016 (Amendment 7)}

Statistical Analysis Plan

{01 Sep 2017, Version 1.0}

9.1.3. Schedule of Study Assessments (Part B, Therapy at 1 and/or 3 mg/kg – Years 2-3, as applicable)

					Schedule of	of Study Asse	ssments						
								ble prior to Pa		-			
Assessments	Wk 54 / Wk 106	Wk 56 / Wk 108	Wk 58 / Wk110	Wk 60 / Wk 112	Wk 62 / Wk 114	Wk 64/ Wk 116	Wk 66/ Wk 118	Wk 68/ Wk 120	Wk 70/ Wk 122	Wk 72/ Wk 124	Wk 74/ Wk 126	Wk 76/ Wk 128	Wk 78/ Wk 130
Visit Window (Days)*	±5	±5	±5	±5	±5	±5	±5	±5	±5	±5	±5	±5	±5
Physical Examination		XP		XP		XP		XP		XP		XP	
Height and Weight		XP		XP		XP		XP		XP		XP	
Vital Signs ¹	Х	Х	Х	Х	Х	Х	х	Х	Х	Х	Х	х	х
12-lead ECG													Х
FDNA													Х
Vineland-II, BSID-III, KABC-II, BOT-2 Brief Form, CSHQ, CCC-2, SBRS, ZBI 12-item, SF-10 ²													х
Hematology, Serum Chemistry (including Coagulation ³), Urinalysis ⁴				X ^P				XP					X ^P
Pregnancy Test (Urine) ⁵		XP		х ^р		XP		х ^р		XP		X ^P	^
Serum and Urine Heparan Sulfate (Total and NRE)				XP		~		XP		~		X	X٩
Serum Ferritin and Chitotriosidase				XP				XP					X ^P
Plasma Glutamic Acid and Glycine				XP				XP					X ^P
Exploratory Serum Biomarkers, including IgG, Inflammatory markers				X ^P				X ^P					X ^P
Serum Pharmacokinetic Profile ⁶													х
SBC-103 ADA ⁷		XP		XP		XP		XP		XP		X ^P	
General Anesthesia/Sedation ⁸							XP						X ^P
Lumbar Puncture ^{3,8,9}							X ^P						XP
Heparan Sulfate (Total and NRE) in CSF							X ^P						XP
Calbindin D, HGF, Tau, pTau, Amyloid β, Albumin, IgG in CSF							X٩						X ^P

Statistical Analysis Plan {01 Sep 2017, Version 1.0}

					Schedule of	of Study Asse	ssments						
			Part B: Thera	apy at 1 and,	/or 3 mg/kg	Years 2 and	3, as applicat	ble prior to Pa	rt C)				
Assessments	Wk 54 / Wk 106	Wk 56 / Wk 108	Wk 58 / Wk110	Wk 60 / Wk 112	Wk 62 / Wk 114	Wk 64/ Wk 116	Wk 66/ Wk 118	Wk 68/ Wk 120	Wk 70/ Wk 122	Wk 72/ Wk 124	Wk 74/ Wk 126	Wk 76/ Wk 128	Wk 78/ Wk 130
Visit Window (Days)*	±5	±5	±5	±5	±5	±5	±5	±5	±5	±5	±5	±5	±5
Glutamic Acids and Glycine in CSF							X ^P						XP
Routine Findings (Cell Counts, Glucose, Protein) in CSF							X٩						X٩
SBC-103 in CSF							X ^P						X ^P
Structural and Diffusion MRI ⁷													
Telephone call ¹⁰													
SBC-103 Dosing	Х	Х	Х	Х	Х	Х	Х	Х	Х	Х	Х	Х	Х
Adverse Events ¹¹		•	•				CONTINUO	US	•		•	•	
Concomitant Medications ¹²	CONTINUOUS												

Key: ADA = anti-drug antibodies; BOT-2 Brief Form = Bruininks-Oseretsky Test of Motor Proficiency, Second Edition, Brief Form; BSID-III = Bayley Scales of Infant and Toddler Development, Third Edition; CCC-2 = Children's Communication Checklist, Second Edition; CSF = cerebrospinal fluid; CSHQ = Children's Sleep Habits Questionnaire; D = day; ECG = electrocardiogram; FDNA = Facial Dysmorphology Novel Analysis; HGF = hepatocyte growth factor; IgG = immunoglobulin G; KABC-II = Kaufman Assessment Battery for Children, Second Edition; NAGLU = alpha-Nacetylglucosaminidase; NRE = non-reducing end; SBRS = Sanfilippo Behavior Rating Scale; SF-10 = 10-item Short Form Health Survey for Children; Vineland-II = Vineland Adaptive Behavior Scales, Second Edition; Wk = week; ZBI = Zarit Burden Interview, 12-item.

* All study visits will be scheduled relative to Day 0; Infusions must be administered at least 10 days apart.

X^P Assessments to be performed pre-dose.

- 1. Vital signs will be taken pre-dose (within approximately 30 minutes), approximately every 15 minutes during infusion and approximately every 15 minutes for 2 hours after completion of the infusion. Vital signs will be obtained after any lumbar puncture as per site standard of care.
- 2. The Vineland-II, BSID-III or KABC-II, BOT-2 Brief Form, and CCC-2 should be administered in-person by an appropriately qualified professional.
- 3. The coagulation laboratory panel should be collected within 48 hours prior to performing the lumbar puncture, and the results should be available prior to sedating/anesthetizing the subject or performing the lumbar puncture. The procedure (including the initiation of sedation/anesthesia) will not commence until the site receives these results and confirms that it is safe for the subject to receive anesthesia/sedation and the lumbar puncture. To facilitate this process, all coagulation panels (as of 23 March 2015) will be drawn and analyzed locally rather than sent to the central

laboratory for analysis.

- 4. Central lab reference ranges will be used throughout the study, including in the event that labs are analyzed locally. All attempts should be made to draw lab samples for central lab analysis when samples are needed for local analysis.
- 5. If a urine sample is not able to be provided, a serum pregnancy test will be performed by a local laboratory.
- 6. Refer to Section 5.2.1.3 for directions and timing of PK sampling.
